#### **10.6.3 Vital Signs**

Descriptive statistics will be presented for systolic blood pressure, diastolic blood pressure, pulse, respiration rate and temperature for baseline, each post-baseline visit, and change from baseline.

#### **10.6.4 ECOG Performance Status**

ECOG performance status scores will be summarized for each treatment arm at each assessed time point. The change in scores from baseline to each assessed time point will also be summarized.

#### **10.6.5 Electrocardiogram (ECG)**

The ECG measurements from this clinical study were performed as per standard of care for routine safety monitoring, rather than for purposes of assessment of potential QTc effect. Since these evaluations may not necessarily be performed under the rigorous conditions expected to lead to meaningful evaluation of QTc data; neither summaries nor statistical analyses will be provided, and these data would not be expected to be useful for meta-analysis with data from other trials.

#### **10.6.6 Antibody Formation**

HSV-1 serostatus will be summarized for each visit for patients who receive talimogene laherparepvec. IgG reactivity with HSV-1 will be determined. The data summaries and baseline serostatus analyses will be performed for IgG. Treatment-emergent adverse events will be summarized for subjects who receive talimogene laherparepvec by baseline HSV-1 serostatus by system organ class and preferred term. In addition, treatment-emergent immune-related adverse events of interest will also be summarized by baseline HSV-1 serostatus and preferred term for patients treated with T-VEC.

The incidence of subjects with herpetic lesions found to be positive for talimogene laherparepvec DNA per qPCR in swab samples collected from lesions suspected to be herpetic in origin and the rate of positive lesions (if any) will be calculated.

Potential or known unintended exposure to talimogene laherparepvec, related suspected signs or symptoms, and detection of talimogene laherparepvec in a subject's household member, caregiver, or healthcare provider will be reported in the final CSR. Listings of reported cases with available qPCR testing results will be provided. Additionally, unintended exposures will be analyzed periodically as part of a program-wide analysis.

#### **10.6.7 Exposure to Investigational Product**

Summary statistics for the total number of talimogene laherparepvec doses administered, total volume of talimogene laherparepvec administered, duration of first talimogene laherparepvec to last talimogene laherparepvec administration, and average volume of talimogene laherparepvec per visit will be provided for subjects who receive talimogene laherparepvec separately for the first dose of talimogene laherparepvec of

$10^6$  PFU/mL and the subsequent doses. The incidence and reasons for drug withdrawal and injection less than 4 ml will be tabulated for subjects who receive talimogene laherparepvec.

A listing of unique manufacturing lot number(s) for talimogene laherparepvec and subject listings of manufacturing lot number(s) of talimogene laherparepvec will be provided.

The protocol specified surgical resection of melanoma tumor lesion(s) will be summarized. For subjects who do not receive the surgery the reason why the surgery is not conducted will also be summarized.

#### **10.6.8 Exposure to Concomitant Medication/Adjuvant Therapy/Subsequent Anti-cancer Therapy**

Prior systemic or regional anti-cancer therapies for current malignancy of melanoma, prior surgeries for current malignancy of melanoma and prior radiation therapy for current malignancy of melanoma will be summarized separately.

The concomitant medications/on-treatment surgery include all /surgery except the protocol specified surgical resection of melanoma lesion(s) after randomization and all medications after randomization before receiving surgery except for talimogene laherparepvec. The number and proportion of subjects receiving any concomitant medication during the treatment period will be summarized by preferred term as coded by the World Health Organization Drug (WHODRUG) dictionary.

The subject incidence and duration of subsequent adjuvant therapy for melanoma will be summarized overall, by type (systemic therapy with radiotherapy, systemic therapy without radiotherapy, radiotherapy without systemic, no subsequent adjuvant therapy at all), and by specific therapy components. **Time to first use of subsequent adjuvant anti-cancer therapy for melanoma will be summarized.**

The subject incidence and time to first use of subsequent non-adjuvant anti-cancer therapy for melanoma will be summarized.

## 11. Changes From Protocol-specified Analyses

The changes from protocol-specified analyses are as following,

- In the statement regarding subjects who are not confirmed to be disease-free post-surgery or who withdraw prior to surgery, failure was changed from “a day after randomization” to “at randomization” for RFS, RRFS, LRFS and DMFS in [section 3.2](#).
- Safety endpoints related to talimogene laherparepvec DNA shedding and potential or known unintended exposure to talimogene laherparepvec were added as safety endpoints. The current protocol mentioned the analysis of these endpoints without specifically claiming them as safety endpoints.

---

**13. Data Not Covered by This Plan**

[figure not shown]
The analysis on exploratory endpoints described in [Section 4.1.3](#) is not covered by this SAP.

[figure not shown]
14. Appendices

---

**Appendix A. Conventions for Clinical Data That Require Imputation for  
Partial or Missing Dates**

---

## Appendix B. Technical Detail and Supplemental Information Regarding Statistical Procedures and Programs

### Code Fragments

#### B.1 Exact Confidence Interval

```
proc freq data=dat1;  
  tables R0/ binomial(exact) alpha=.2;  
  by TRTGRP;  
run;
```

#### B.2 Nair Equal-Precision Band

```
proc lifetest data=dat1 plots=survival(cb=ep test);  
  time OS * CENSOR(1);  
  strata TRTGRP;  
run;
```

#### B.3 Bootstrap for Confidence Interval of Quantile Difference per K-M Estimate

```
%let rep = 100;  
proc surveysselect data= os out=bootsample  
  seed = 1347 method = urs  
  samprate = 1 outhits rep = &rep;  
run;  
ods listing close;  
  
ods output Quartiles=TimeToDeath;  
proc lifetest data=bootsample alpha=0.2 ALPHAQT=0.2 plots=(s);  
  time OSM*CENSOR(1);  
  strata TRTGRP;  
  by Replicate;  
run;  
ods output close;
```

#### B.4 Wilson's Score Method With Continuity Correction

Macro and Sample Code for Wilson's score method with continuity correction

- S1 is the numerator and N1 is the denominator for T-VEC; S2 is the numerator and N2 is the denominator for GM-CSF
- There are variables P1, P2 , LL and UL.
- The percentage difference is the P1-P2 and 95% CI is (LL, UL)

```
%macro method11(ds=,  
  dsout=,  
  by=,  
  cc=0.80);  
  
  data &dsout;  
  length s1 n1 p1 s2 n2 p2 LL UL cc 8;  
  set &ds;  
  retain cc &cc;  
  array nn{2} n1 n2;  
  array s{2} s1 s2;  
  array p{2} p1 p2;  
  array q{2} _temporary_;
```

```
array np{2} _temporary_;
array nq{2} _temporary_;
array l{2} _temporary_;
array u{2} _temporary_;
ca2=probit(0.5 + cc/2);
ca2sq=ca2*ca2;
do i=1 to 2;
  p{i}=s{i}/nn{i};;
  q{i}=1-p{i};;
  nq{i}=nn{i}*q{i};
  np{i}=nn{i}*p{i};
  if p{i}=0 then l{i}=0;
  else l{i}=(((2*np{i})+(ca2sq-1))-(ca2*(sqrt((ca2sq-(2+(1/nn{i}))+
((4*p{i})*(nq{i}+1)))))))/(2*(nn{i}+ca2sq)) ;
  if p{i}=1 then u{i}=1;
  else u{i}=(((2*np{i})+(ca2sq+1))+(ca2*(sqrt((ca2sq+(2-(1/nn{i}))+
((4*p{i})*(nq{i}-1)))))))/(2*(nn{i}+ca2sq)) ;
  end;
  d=sqrt((p{1}-l{1})**2+(u{2}-p{2})**2);
  e=sqrt((p{2}-l{2})**2+(u{1}-p{1})**2);
  LL=p{1}-p{2}-d;
  UL=p{1}-p{2}+e;
* keep s1 n1 p1 s2 n2 p2 LL UL cc;
label s1='Number of Sample from Population 1'
      n1='Number of Population 1'
      p1='Proportion 1 = s1 / n1 '
      s2='Number of Sample from Population 2'
      n2='Number of Population 2'
      p2='Proportion 2 = s2 / n2'
      ll='Lower limit of interval estimation for difference'
      ul='Upper limit of interval estimation for difference'
      cc='Confidence coefficient';

run;

%if %length(&by)>0 %then %do;
  proc sort data=&dsout;
    by &by;
  run;
%end;

title1 "Comparison of two independent proportions using continuity
correction" ;
title2 'NEWCOMBER METHOD 11 : Example H ' ;
title3 "LL UL &cc% CI for Difference between Independent
Proportions";
proc print data=&dsout label;
  var &by n1 s1 p1 n2 s2 p2 LL UL cc;
run;
%mend method11;

data dsin;
  input n1 n2 s1 s2;
cards;
25 50 5 4.25;
run;

%method11(ds=dsin, dsout=dsout, by=, cc=0.95);
```

## B.5 Assumption of non-proportional Hazard: Treatment\*log (time) Interaction in the Cox Model

```
proc phreg data=dat1;
  model OS * CENSOR(1) = TRTGRP TRTGRP_T / ties=exact rl=pl;
  TRTGRP_T = TRTGRP *log(OS);
  strata randomization_strata;
  proportionality_test: test TRTGRP_T;
run;
```

## B.6 Assumption of non-proportional Hazard: Kolmogorov-type Supremum Test

```
ods select cumulativeresiduals scoreprocess;
proc phreg data=dat1;
  model OS*CENSOR(1) = TRTGRP / ties=exact rl=pl;
  * Delete strata statement to assess overall proportional hazards;
  strata randomization_strata;
  assess ph / resample seed=1234;
run;
```

## B.7 Piecewise Cox Model

```
proc phreg data= dat1;
  model OS*CENSOR(1) = TRTGRP1 TRTGRP2 TRTGRP3 / ties=exact rl=pl;
  TRTGRP1 = TRTGRP *(OS lt 12);
  TRTGRP2 = TRTGRP *(12 le OS lt 24);
  TRTGRP3 = TRTGRP *(24 le OS);
  strata randomization_strata;
run;
```

## B.8 Estimates Crude Cumulative Incidence Function and Test Equality of Cumulative Incidence (Gray's Test)

```
proc lifetest data=dat1;
  time LRFS*Status(0)/eventcode=1;
  strata TRTGRP / order=internal;
  *test for overall difference between groups;

  *strata randomization_strata/group=TRTGRP order=internal;
  * stratified test;
run;

/* The variable Status has three values: 0 for censored observations, 1
for subjects with event of interest (e.g. local recurrence for LRFS),
and 2 for patients who experienced competing risk */
```

## B.9 Fine-Gray Subdistribution Proportional Hazards Model

```
Proc phreg data=dat1 ;
  class TRTGRP (order=internal ref=first) param=galm;
  model LRFS*Status(0)= TRTGRP x1 x2 / eventcode=1;
  hazardratio 'Subdistribution Hazards' TRTGRP;
  strata randomization_strata;
  * Delete strata statement to assess overall proportional hazards;
  * x1, x2 are covariates.
```

```
run;
```

```
/* The variable Status has three values: 0 for censored observations, 1  
for subjects with event of interest (e.g. local recurrence for LRFS),  
and 2 for patients who experienced competing risk. */
```

## B.10 IPCW

```
/*Model probability of not receiving all or selected actual adjuvant  
therapy for melanoma including time-independent covariate(s)*/  
proc logistic data=time_indep;
```

```
  class <categorical time-independent covariate(s)>;  
  model subther(event='0') = <time-independent covariate(s)>;  
  output out=out1 prob=num;  
run;
```

```
proc sort data = time_dep;  
  by descending subther;  
run;
```

```
/*Model probability of not receiving all or selected actual adjuvant  
therapy for melanoma including time-independent covariate(s) and time-  
dependent covariate(s)*/
```

```
proc genmod data = time_dep descending order=data;  
  class <categorical time-independent covariate(s)> <categorical time-  
dependent covariate(s)> usubjid;  
  model subther = <time-independent covariate(s)> <time-dependent  
covariate(s)> / d=binomial link=logit;  
  repeated subject=usubjid;  
  output out=out2 prob=den;  
run;
```

```
proc sort data=out1;by usubjid;run;  
proc sort data=out2;by usubjid;run;
```

```
/*Calculate weights*/  
data dat1;  
  merge out1 out2;  
  by usubjid;  
run;
```

```
data dat2;  
  set dat1;  
  by usubjid;  
  retain w_num w_den;  
  if first.usubjid then do;  
    w_num = 1;  
    w_den = 1;  
  end;  
  w_num = w_num*num;  
  w_den = w_den*den;  
  
  if subther = 1 then weights = (1-w_num)/(1-w_den);  
  else if subther = 0 then weights = w_num/w_denom;  
run;
```

---

```
data dat3;
  merge dat2(in=a) adam.adtte(in=b where=(paramcd='RFSI' keep=usubjid
paramcd aval cnsr);
  by usubjid;
  if a and b;
run;

/*HR and corresponding CI using IPCW*/
proc phreg data = dat3;
  class trt01p(ref="SURGERY");
  model aval*cnsr(1) = trt01p;
  freq weights / nottruncate;
  hazardratio trt01p / alpha=0.05 cl=wald diff=ref;
  strata <stratification factors>;
run;
```

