### 10.5.1 Analyses of Primary Efficacy Endpoint(s)

An overall between-group difference in RFS will be evaluated with a log-rank test and corresponding proportional hazards model without stratification. Sensitivity analyses, using alternate definitions of RFS as defined in [section 4.1.1](#), will be evaluated in the same manner. Additionally, for RFS, a log-rank test and proportional hazards model with stratification by the two randomization factors will also be conducted.

A sensitivity analysis will be performed censoring RFS at the start of all or selected actual adjuvant therapy for melanoma. However, censoring at start of all or selected adjuvant therapy for melanoma may introduce dependent censoring as the ability to receive further adjuvant therapy will likely be correlated with RFS. An inverse probability censoring weighting (IPCW) method (Robins, et al) which may reduce the potential bias will also be used to obtain an estimate of the treatment effect on RFS and may include baseline covariates in [Section 4.2](#).

In order to assess the impact of imbalances in the type of adjuvant therapy, a **stratified** Cox model will be repeated stratifying actual adjuvant systemic therapy (yes vs no). A KM time to event plot for RFS will be generated by 4 groups (Arm 1 with adjuvant systemic therapy, Arm 1 without adjuvant systemic therapy, Arm 2 with adjuvant systemic therapy, Arm 2 without adjuvant systemic therapy), and 2 separate KM plots will be generated by randomized treatment group in subjects with and without adjuvant systemic therapy respectively. If warranted due to actual adjuvant therapy (eg, the planned adjuvant therapy stratification factor is discordant with the actual for > 10% of all subjects), the stratified Cox model analysis will be repeated stratifying on **actual** adjuvant therapy type (**adjuvant systemic therapy with or without radiotherapy vs radiotherapy without adjuvant systemic therapy vs none**).

**To explore the prognostic and/or predictive value of the covariates listed in [Section 4.2](#), univariate and multivariate proportional hazards models without stratification will be used. Subgroup analyses will be evaluated with a log-rank test and corresponding proportional hazards model without stratification.**

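### SAP Appendix B.10 builds the IPCW weights incorrectly, so the weighted hazard ratios can keep or enlarge the dependent-censoring bias they are meant to reduce

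*SAP*

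**What the plan says.** SAP Section 10.5.1 notes that censoring RFS at adjuvant therapy may be dependent. It plans IPCW to "obtain an estimate of the treatment effect on RFS and may include baseline covariates" from Section 4.2. Section 10.5.2 plans the same for LRFS, with similar analyses for DMFS and RRFS. The construction of the weights appears only in Appendix B.10:

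- **Numerator:** "proc logistic data=time_indep", with "model subther(event='0') = <time-independent covariate(s)>".
- **Denominator:** a repeated-measures binomial model on `time_dep`, beginning "model subther = <time-independent covariate(s)> <time-dependent". It uses the same baseline placeholder plus time-dependent covariates.
- **Combination:** the two outputs are merged by `usubjid` alone, and both probabilities are accumulated as running products over a subject's rows. `time_dep` was sorted by descending therapy status, and the denominator output is then sorted by `usubjid` only.
- **Weights:** "if subther = 1 then weights = (1-w_num)/(1-w_den") for rows on therapy, and "else if subther = 0 then weights = w_num/w_denom" for rows without it.
- **Outcome model:** "model aval*cnsr(1) = trt01p" with "strata <stratification factors>". Each row carries the subject's single `aval` and `cnsr`; there are no start-stop intervals.

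**The concern.** A stabilised weight may condition its numerator only on variables that the outcome model also conditions on. A baseline covariate that is in both weight models but not in the outcome model is not properly adjusted for anywhere. Section 4.2 lists 12 covariates. Two are the randomization factors, which the STRATA statement presumably covers. The other ten, including ECOG, BRAF status, tumor number and SPD, fall in this gap.

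Three coding faults come on top:

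- A subject-level probability is compounded at each visit.
- Nothing orders the visits before a cumulative product.
- `w_denom` is undefined; the retained variable is `w_den`.

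At stake is whether the weighted hazard ratio can be read as reducing the bias from adjuvant therapy. Selection that differs by arm is plausible: the trial is open-label, adjuvant therapy is at the investigator's discretion after surgery, and pCR is assessed in Arm 1 only.

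**Working it through.** **Anchor.** The documents give no figure for the IPCW analysis, so SAP Table 1 was reproduced to set the scale. HR = ln(0.70)/ln(0.60) = 0.698. With 64 events the SE of log HR is 2/√64 = 0.25. The 80% CI is 0.698 × exp(±1.2816 × 0.25) = 0.51 to 0.96. The probability that it lies below 1 is Φ(0.359/0.25 − 1.2816) = 0.56. All match.

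**Algebra.** Take one baseline covariate x. Let q(x) be the per-visit probability of not starting therapy and p(x) the subject-level probability of never starting.

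- Numerator fitted per visit on x alone, with no time-dependent term: weight at visit k = q(x)^k / q(x)^k = 1, which is plain censoring.
- B.10 as coded, if `time_indep` has one row per subject: weight at visit k = p(x)^k / q(x)^k. Since p(x) < q(x) over more than one visit, the weight shrinks with k, at a rate that depends on x.

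For example, in the main scenario below 32.8% start therapy, so p averages 1 − 0.328 = 0.672. At that value the numerator is 0.672 on row 1, 0.672^4 = 0.204 on row 4 and 0.672^8 = 0.042 on row 8.

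**As printed.** `w_denom` is never assigned, so every row with `subther = 0` has a missing weight. The rest of the check reads it as `w_den`.

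**Simulation.** Inputs from the SAP: Arm 2 two-year RFS about 0.60 and HR 0.70. Assumed: 3-monthly visits, and a binary baseline covariate X with RFS HR 1.5 to 2.5 that drives adjuvant uptake. There were 400,000 to 1,000,000 subjects per scenario, and pooled logistic regression stood in for the repeated-measures model. Target means the HR without adjuvant therapy. Arm is in the weight models except where stated, and X is outside the strata.

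| Scenario | Target | Plain censoring | Per-visit numerator, arm only | B.10 weights, start-stop rows | B.10 weights, rows as printed |
|---|---|---|---|---|---|
| X drives uptake in Arm 2 only | 0.709 | 0.776 | 0.709 | 0.949 | 1.036 |
| Opposite directions by arm | 0.714 | 0.852 | 0.714 | 1.258 | 1.269 |
| X drives uptake more in Arm 1 | 0.712 | 0.649 | 0.710 | 0.506 | 0.463 |
| Weaker covariate (RFS HR 1.5) | 0.699 | 0.712 | 0.697 | 0.756 | 0.771 |
| Same dependence in both arms | 0.713 | 0.712 | 0.713 | 0.692 | 0.687 |
| As row 1, arm left out of weight models | 0.708 | 0.773 | 0.773 | 0.738 | 0.755 |
| Time-dependent covariate only | 0.735 | 0.804 | 0.731 | 0.681 | 0.808 |

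- A per-visit numerator on the same baseline covariates as the denominator reproduces plain censoring in the first three rows (0.776, 0.852, 0.649). The bias is kept.
- Mean B.10 weight in row 1: 0.72 at visit 1, 0.34 at visit 4 and 0.17 at visit 8. Proper weights average 1.01, 1.01 and 0.97.
- With X in the strata and start-stop rows, the B.10 weights give 0.704, 0.705 and 0.703 in the first three rows, against conditional targets of 0.699, 0.705 and 0.700. With rows as printed they give 0.728, 0.662 and 0.646.
- In row 6 the arm-only column also fails, because arm is missing from the denominator.

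A second simulation used other assumptions: true HR 1.00, covariate RFS HR 2.0 to 2.5, and uptake of about 40% in Arm 2 and 21% in Arm 1 with stronger selection in Arm 2. Plain censoring gave 1.11 to 1.15. B.10 weights gave 1.22 to 1.31 with arm in the weight models and 1.05 to 1.08 without it. An arm-and-visit numerator gave 1.00 to 1.01. Under milder selection the figures were 1.02 to 1.03 (plain), 1.04 to 1.05 (B.10 with arm) and 1.00 (correct).

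**The case against.** The strongest reply is that B.10 is a fragment with placeholders, supporting one sensitivity analysis in a descriptive trial. Section 10.5.1 claims only that IPCW may reduce bias, and the SAP also examines adjuvant therapy by stratifying on actual use, by Kaplan-Meier curves within adjuvant groups and by other censoring rules. That limits the stakes. It does not make the weights right, and no other text says how to build them.

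Three stronger readings are tempting, and the documents do not support them.

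- **No Section 4.2 covariate is conditioned on.** The STRATA line covers disease stage and planned adjuvant therapy, if those fill its placeholder. Planned therapy is an obvious predictor of actual therapy. For covariates in the strata, and with start-stop rows, the weight errors do almost no harm.
- **Every weight equals 1.** That needs a per-visit numerator and no time-dependent term. B.10 prints neither: it lists time-dependent covariates in the denominator, and its numerator is not fitted on visit rows.
- **The weighted hazard ratio always keeps or enlarges the bias.** Without arm in the weight models, the B.10 weights with start-stop rows move 0.773 to 0.738 against a target of 0.708. Randomized arm is not in the Section 4.2 list, so this case is possible. Under equal selection the error is small.

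The selection strengths are assumptions, since the documents give none. One row per subject in `time_indep` is inferred from its name and from the merge by `usubjid`.

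**Conclusion.** The point holds in limited form. Followed as printed, B.10 gives wrong weights in four ways:

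1. Covariates outside the strata are in both weight models but not in the outcome model.
2. The numerator, apparently subject-level, is compounded per visit.
3. Rows are not sorted by visit before the product.
4. Weights are missing wherever therapy has not started.

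With `w_denom` repaired and start-stop rows used, the hazard ratio can keep or enlarge the bias when a covariate outside the strata drives adjuvant uptake differently by arm.

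The size depends on the assumed selection. On the log scale the error is ln(0.949/0.709) = 0.29 in the main scenario, ln(0.756/0.699) = 0.08 with the weaker covariate, and ln(0.692/0.713) = −0.03 under equal selection. The planned SE is 0.25 at 64 events, and an analysis censored at adjuvant therapy would have fewer events. Only the first would be conspicuous in this trial.

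The IPCW sensitivity analyses of RFS, LRFS, DMFS and RRFS are affected. The primary RFS analysis is not.

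**What to change.** Rewrite the weight steps of Appendix B.10:

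- Fit the numerator on the same per-visit rows as the denominator, using only randomized arm, visit and the stratification factors in the STRATA statement.
- In the denominator, use those terms plus the other Section 4.2 covariates and any time-dependent covariates. Let covariate effects differ by arm where selection may. Alternatively, add every numerator covariate to the outcome Cox model.
- Sort by `usubjid` and visit before forming the products, and replace `w_denom` with `w_den`.
- Use start-stop rows censored at the start of adjuvant therapy, so that rows on therapy are not weighted back in.
- Report the mean weight by visit; it should stay near 1.

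Name the time-dependent covariates, or say that there are none. The cost is a few lines of code and a sentence in Section 10.5.1. No data collection, sample size or primary analysis changes.

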**Table 2. Study Design Characteristics Example Endpoint Summary Table**

Endpoint	Primary Summary and Analysis Method	Sensitivity Analysis
Primary Endpoint		

 
• RFS
 
	
 
• Log-rank test and 80% CI for the treatment hazard ratio from a proportional hazards model without stratification in the ITT analysis set.
 
• Kaplan-Meier (K-M) estimation by randomized treatment arm.
 
• Simultaneous 80% confidence band for each arm KM estimate from 1 to 5 years per equal-precision band method.
 
• 80% CI for K-M quartiles by arm (where estimable) per Brookmeyer & Crowley.
 
• 80% CI for between-arm quartile difference in KM estimate via bootstrap.
 
	
 
• Repeat with stratification by the two randomization factors
 
• If 10% or more of the overall recurrence (both arms combined) occur within the first 6 months post-surgery, the stratified analysis will be repeated with stratified piece-wise Cox model to estimate within interval hazard ratios adjusting for randomization factors.
 
• Estimate the Cox model hazard ratio with Robins IPCW weighting censoring RFS at the start of all or selected adjuvant therapy for melanoma.
 
• If warranted (eg, the planned adjuvant therapy stratification factor is discordant with the actual for > 10% of all subjects), the stratified analysis will be repeated replacing planned adjuvant therapy with actual adjuvant therapy and/or adjuvant therapy containing selected types of systemic therapy, including immunotherapy.
 
• Cox model and KM analysis of RFS according to randomized treatment and actual adjuvant systemic therapy (yes vs no) with 3 comparisons: all subjects, those with adjuvant systemic therapy, and those without adjuvant systemic therapy.
 
• Repeat with and/or without stratification by the two randomization factors in the efficacy analysis set, if necessary.
 
• Univariate and multivariate proportional hazards models without stratification may be used to explore the prognostic and/or predictive value of baseline covariates using primary endpoint definition and alternative endpoint definition #1 in Section 4.1.1.
 
• Subgroup analyses will be evaluated with a log-rank test and corresponding proportional hazard model without stratification using primary endpoint definition and alternative endpoint definition #1 in Section 4.1.1.
 
• Repeat subgroup analyses with a log-rank test and proportional hazards model with stratification by two randomization factors.
 
• Repeat using sensitivity analysis alternative endpoint definitions (see Section 4.1.1).
 
• Repeat based on the type of anti-cancer therapy received: any subsequent anti-cancer therapy, adjuvant anti-cancer therapy for melanoma, non-adjuvant anti-cancer therapy for melanoma using primary endpoint definition and alternative definition # 1 in Section 4.1.1. Subjects who receive the respective subsequent anti-cancer therapy type prior to an RFS event will be censored at the last evaluable tumor assessment prior to receiving the respective subsequent anti-cancer therapy type.
 

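### SAP Appendix B.10 does not carry out the IPCW analysis planned in 10.5.1 and its standard error is invalid; separately, 9.4.3(c) and Table 2 treat non-adjuvant therapy in opposite ways

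*SAP*

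**What the plan says.** SAP 10.5.1 and the RFS row of Table 2 ask for RFS censored at the start of all or selected adjuvant therapy. Because 10.5.1 expects that censoring to be dependent, it adds an IPCW estimate. SAP 10.5.2 asks for the same on LRFS, DMFS and RRFS.

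Appendix B.10 gives the code:

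- **Weights.** On-therapy rows receive "if subther = 1 then weights = (1-w_num)/(1-w_den" (closing parenthesis follows). Off-therapy rows receive "else if subther = 0 then weights = w_num/w_denom", although the variable created earlier is `w_den`.
- **Rows.** The denominator model has "repeated subject=usubjid", and the weights are running products reset at each new subject, so several rows per subject are intended. The denominator data are sorted "by descending subther" and the output by subject only.
- **Outcome model.** The subject's single `aval` and `cnsr` from parameter RFSI are merged by subject onto the weight rows. The model is "model aval*cnsr(1) = trt01p" with "freq weights / nottruncate" and "hazardratio trt01p / alpha=0.05 cl=wald diff=ref".

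For the primary RFS comparison, Table 2 specifies "80% CI for the treatment hazard ratio from a proportional hazards model without stratification".

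On subsequent therapy, SAP 9.4.3 splits the sensitivity analysis into (a) any, (b) adjuvant and (c) non-adjuvant. It makes (c) an event at the last evaluable assessment before the therapy. Table 2 lists the same three types and censors all of them at that assessment.

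**The concern.** IPCW needs follow-up that stops when therapy starts, one contribution per subject per interval, and a variance that allows for the weights and for repeated rows. B.10 lacks all three as written. A subject with several rows enters the Cox model as several people, each with the full follow-up time and the same event.

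Three further features matter:

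- On-therapy rows carry a weight and are not dropped.
- No sort contains time, so for a subject who starts therapy the on-therapy row moves ahead of the earlier rows before the running products are formed.
- If the numerator data set has one row per subject, its probability is multiplied in again on every row.

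Adjuvant therapy is at the investigator's discretion in an open-label trial. The SAP has other checks on it (simple censoring, Cox stratified by actual therapy, Kaplan-Meier curves by actual therapy). IPCW is the only one aimed at the dependent censoring that 10.5.1 names. An interval of the wrong width would mislead readers of that check.

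**Working it through.** **1. The plan's own figure.** Inputs from SAP 3.2 and Table 1: 2-year RFS 0.70 and 0.60, 64 events.

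- HR = ln 0.70 / ln 0.60 = 0.357/0.511 = 0.698
- SE = 2/√64 = 0.25
- 80% CI = 0.698 × exp(±1.282 × 0.25) = 0.507 to 0.962
- Probability that the CI lies below 1 = Φ(0.359/0.25 − 1.282) = 0.562

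Table 1 states 0.70, 0.51 to 0.96 and 0.56. The documents give no figure for the IPCW analysis.

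**2. Row duplication alone.** With k identical rows per subject and all weights 1, the model SE is 0.25/√k and true coverage of a nominal 95% CI is 2Φ(1.96/√k) − 1.

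| k | Model SE | 95% CI at HR 0.698 | True coverage |
|---|---|---|---|
| 1 | 0.250 | 0.43–1.14 | 95% |
| 4 | 0.125 | 0.55–0.89 | 67% |
| 8 | 0.088 | 0.59–0.83 | 51% |

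**3. An opposing effect.** If the numerator is fitted once per subject, the running product makes it num to the power k. At 67% use, num averages about 0.33, so by the fourth row it is 0.33⁴ = 0.012. A numerator fitted per interval and cumulated would not fall below about 0.33. This shrinks the weights and works against step 2, so the direction is not fixed in advance.

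**4. Simulation at low to moderate use.** From the documents: 150 subjects 1:1, exponential RFS as above, 18-month accrual (Protocol 3.5.1), analysis 2 years after the last randomization, 10% drop-out, and surgery at weeks 13–18 or 1–6. Assumed, because not given: adjuvant use of 19%, 37% or 54% before an RFS event or censoring; start 4–20 weeks after surgery; use related to one baseline covariate; no therapy effect; row spacing. With 2,000 trials per use rate this gave 63 events and probability 0.55, against 64 and 0.56 in Table 1.

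B.10 was read favourably: misprints fixed, rows in time order and ending at therapy start, RFSI censored there. Ranges are over the use rates and two numerator readings (per subject, per interval).

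| Rows | Mean rows per subject | Model SE / true SD | 95% CI coverage | 80% CI coverage |
|---|---|---|---|---|
| 3-monthly | 4.6–7.0 | 0.33–0.82 | 49–91% | 34–71% |
| 6-monthly | 2.6–3.8 | 0.47–0.80 | 65–90% | 45–69% |
| 12-monthly | 1.6–2.2 | 0.63–0.83 | 79–91% | 58–71% |
| One per subject | 1.0 | 0.98–1.00 | 95–96% | 80–81% |

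A repeat gave about 48–91% for 95% coverage. Mean log HR was −0.32 to −0.40 against a true −0.36. If RFSI is not censored at therapy start, 95% coverage is 50–77%, 66–87%, 80–92% and 95% in the same row order. Person-interval IPCW with robust SE on the same data covers 95–96%.

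Example at HR 0.70, 37% use, per-interval numerator: B.10 gives a 95% CI of 0.54–0.91 (3-monthly), 0.49–0.99 (6-monthly) or 0.45–1.09 (12-monthly), against 0.38–1.30 with the correct structure.

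A second set (300 trials per setting, 3-month rows, about 28% use) gave 49–62% with rows ending at therapy start and 23–41% with rows kept to the end of follow-up. Correctly structured IPCW covered 89–95% across that set.

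**5. Higher use.** Per-subject numerator, RFSI censored at therapy start, time-ordered rows ending there, 600 trials per setting:

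| Adjuvant use | 36% | 55% | 68% | 77% | 84% |
|---|---|---|---|---|---|
| SE/SD, 3-monthly | 0.56 | 0.74 | 0.99 | 1.18 | 1.50 |
| 95% coverage, 3-monthly | 74% | 88% | 96% | 98% | 100% |
| SE/SD, 6-monthly | 0.65 | 0.79 | 0.92 | 1.00 | 1.22 |

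A repeat at 3-monthly rows gave SE/SD 1.0 at 67% use and 1.7 at 83%, with mean log HR −0.23 against −0.36. The crossover is itself layout-dependent. At 68–69% use, with the row order that B.10's sorts leave, the second set still covered only 73–74%.

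**6. Rule (c).** Section 9.4.3 and Table 2 name the same therapy type and the same assessment date; one says event, the other censored. SAP Section 11 does not mention it. Section 6 calls any therapy after surgery and before recurrence adjuvant. Rules 2 and 3 of 4.1.1 already make non-R0 subjects and pre-surgery withdrawals events at randomization. Few subjects may fall under (c), and no effect size can be derived.

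**The case against.** The strongest case is that Appendix B is headed as code fragments. B.10 contains placeholders, B.4 still names another trial's comparator, and 10.5.1 does not link to B.10. It is an unfinished template for one of several sensitivity analyses in a descriptive trial, and SAP 9.7 requires output to be verified. That limits the severity. It does not remove the point, because no other text gives the weights, data layout or variance. One row per subject would avoid the duplication, but it does not fit the repeated-subject statement and running products.

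Several stronger readings are tempting and are not supported:

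- **That B.10 always gives too narrow an interval.** Step 5 shows a multi-row layout where it is about right or too wide.
- **That post-therapy follow-up necessarily stays in.** If RFSI is already censored at therapy start, it does not. The SAP does not say. The on-therapy rows and duplicated outcomes remain either way.
- **That the sort order drives the error.** At 36% and 55% use with 3-monthly rows, the code's own order moved SE/SD only from 0.56 to 0.58 and from 0.74 to 0.78.
- **That the 95% level in B.10 is an error.** The 80% level in Table 2 belongs to the primary hazard ratio. No level is stated for the IPCW hazard ratio, and 10.5.2 uses 95% for the subdistribution hazard ratios.
- **That the misprints are the fault.** The unbalanced parenthesis and the misspelled option may come from reading the PDF.

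**Conclusion.** With its misprints repaired, B.10 is not the analysis described in 10.5.1 and Table 2, and its model-based standard error is invalid. Confidence in this structural fault is high, because it can be read from the code.

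Confidence in its size and direction is moderate. Both depend on row spacing, numerator layout, the definition of RFSI and the rate of adjuvant use, none of which the SAP gives. At an assumed 19–54% use the interval was too narrow in every multi-row layout tried. At higher use the error can vanish or reverse, and with 3-monthly rows the log HR can be pulled towards 0. Correctly structured IPCW covered 89–96% across the simulations.

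The event-versus-censored conflict for (c) is a direct contradiction, probably touching few subjects. A reader might infer that the event rule in 9.4.3 must be the intended one; the documents support only that the two places be reconciled. A reader might also infer that the primary result is in doubt. It is not: the primary ITT Cox model uses neither B.10 nor rule (c).

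**What to change.** Rewrite B.10 as follows:

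- Use time-ordered person-interval data that end at the start of adjuvant therapy.
- Fit numerator and denominator per interval and cumulate both over the same intervals.
- Use (start, stop] rows with the event only on the last row.
- Replace FREQ by WEIGHT, and add COVS(AGGREGATE) with ID usubjid.
- Define `time_indep`, `time_dep` (row spacing and time-dependent covariates; 10.5.1 names only baseline ones) and RFSI.
- State the CI level: 80% if the result is to be read beside the primary hazard ratio.

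Separately, state one rule for (c) in both 9.4.3 and Table 2, and define non-adjuvant therapy in Section 6 so that (b) and (c) do not overlap.

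The cost is an SAP appendix and wording change plus programming time. No new data are needed.
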